5.1.2. Treatment

A flow chart of study activities is presented in [Figure 1](#).

For subjects randomized to quizartinib the starting dose will be 30 mg/day unless the subject is receiving concurrent therapy with a strong CYP3A4 inhibitor, in which case the starting dose will be 20 mg/day. The dose will be taken in the morning with or without food over continuous 28-day cycles. If the subject omits taking quizartinib in the morning, it may be taken later in the day (until midnight), otherwise the dose should be considered missed. If the subject vomits after

taking quizartinib, no replacement dose should be given. Detailed information on quizartinib dosing is provided in Section 5.6.4.1.

The dose of quizartinib will be increased at Day 16 or Cycle 2 Day 1 according to the criteria specified in Section 5.6.4.3. Following dose escalation, triplicate ECG determinations should be performed at least once weekly for 2 weeks to monitor QTcF prolongation.

If necessary, the dose of quizartinib may be reduced according to the criteria described in Section 5.6.4.4.

See also Section 8.5 for details of QTcF management when prolongation is observed.

[figure not shown]
In subjects receiving quizartinib or LoDAC, treatment should continue until there is no longer clinical benefit from therapy, or until unacceptable toxicity occurs. For subjects receiving LoDAC the initiation of cycles may be delayed for up to 14 days to allow for recovery from toxicity.

Subjects that receive either quizartinib or LoDAC will be assessed for response on Day 1 of Cycle 2 and Day 1 of Cycle 3 as well as on Day 1 of each subsequent cycle unless the subject has already achieved CR, CRp, or CRi. In that event, bone marrow testing will be repeated after every 3 subsequent cycles, unless there is evidence of relapse.

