- ^g A bone marrow and peripheral blood sample should be obtained at screening (at approximately the same time) for determination of FLT3-ITD status. A bone marrow sample should be obtained at treatment discontinuation or relapse. The sample may also be tested for FLT3 point mutations and mutations in other AML-associated genes.
- ^h If consent is provided, blood sample (Pax gene DNA, Pax gene RNA, and PBMC) and buccal swab on Day 1 of Cycle 1 before dosing.
- ⁱ Additional study site visits are required for subjects receiving MEC (Days 1 through 5) or FLAG-IDA (Days 1 through 6). MEC and FLAG-IDA are administered for up to 2 cycles, depending on response and safety assessments.
- ^j Treatment with LoDAC may continue past Cycle 2 and subsequent cycles will follow same procedures as Cycle 2. . Low dose cytarabine should be administered for 10 days in a 28 day cycle in the clinic unless arrangements can be made for administration outside of the clinic. If dosed outside the clinic, a review of medication returned and assessment of compliance must be conducted at the beginning of each cycle.

Table 6 Schedule of Activities and Assessments After Treatment

Activity	End of Treatment Visit ^a	Cross-Over ^f	30-Day Follow-Up	Long-term Follow-Up	Early Termination / End of Study ^h
Written informed consent		X			
Physical examination	X ^b	X			
Vital sign determinations	X ^b	X			
ECOG performance status determination	X ^b	X			
Assessment of concomitant medications	X	X	X		X
Serum pregnancy test for women of childbearing potential	X				
Determination of coagulation profile (PT/INR)		X			
12-lead ECG (triplicate)	X	X			
Clinical laboratory tests (hematology; chemistry; urinalysis)	X ^b	X ^g			
Bone marrow aspiration or biopsy	X ^c				
Assessment of FLT3 mutations using bone marrow	X ^d				
Collection of blood for pharmacogenomic and proteomic determinations	X ^e				
AE/SAE assessment	X	X	X ^h		X
Review of returned study medication and assessment of compliance, for subjects receiving quizartinib or LoDAC	X				X ⁱ
Determination of remission status, subsequent antileukemic treatments and their outcomes, and survival		X	X ^h	X ⁱ	
Reason for withdrawal					X

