8. SAFETY EVALUATION

All subjects receiving at least 1 dose of quizartinib or salvage chemotherapy will be evaluable for safety and defined as the Safety Analysis Set. Safety will be assessed with physical examinations, vital sign determinations, 12-lead ECGs, AE evaluations, and clinical laboratory tests (hematology, serum chemistry, and urinalysis results). The safety data will also be summarized for pre-defined sub-groups.

Study drug toxicity will be assessed continuously. AEs will be evaluated during the study according to NCI CTCAE v4.03 until 30 days after the last dose of study treatment.

Subjects should be instructed to report any new AE or worsening of an existing AE immediately.

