13.3. Sample Size Determination

Calculation of sample size is based on comparison of OS, the primary efficacy endpoint, in the 2 treatment groups (quizartinib and salvage chemotherapy) at a 2-sided significance level of 0.05, assuming that median survival is 3.9 months in the salvage chemotherapy group with an increase to 6 months, in the quizartinib group (hazard ratio 0.65). A total of 280 events (deaths) are necessary to meet a power requirement of 90%, given an interim analysis planned at 140 events (deaths) with O'Brien-Fleming boundary for superior efficacy and a conditional power (CP) of 10% for futility. For the purpose of sample size calculation, subjects are assumed to be accrued at a rate of 19.2 per month with a drop-out rate of 10%. The target accrual is a total of approximately 363 subjects randomized in a 2:1 ratio (242 subjects in the quizartinib group and 121 in the salvage chemotherapy group) over 17 months, to reach required number of events in a reasonable timeframe and to compensate for drop-outs. All calculations for sample size were performed using East® 6.3.

One formal interim analysis will be performed by an independent SAC and evaluated by an independent DMC according to statistical procedures defined a priori. At the interim analysis, the DMC may recommend 3 potential study options: (1) the study should be stopped due to futility; (2) the study should be stopped for superior efficacy in the quizartinib arm; or (3) the study should continue as planned to the total targeted number of 280 events.

It will be impossible to blind treatment allocations for individual subjects because of different treatment administration schedules and adverse events between the 2 study arms. However, the primary endpoint of survival is a robust endpoint and not susceptible to bias resulting from lack of blinding. Additionally, the Sponsor will not have access to aggregate efficacy data except when data from both treatment and control arms are combined. In addition, data relating to the primary endpoint of survival will be restricted so that the Sponsor will not have access to follow up data on individual subjects after 30 days of discontinuing study treatment. Approximately 80% of events will occur in this long term follow up period and so the Sponsor will be blinded to the primary endpoint of the study.

Randomization will be stratified by prior therapy and response, and pre-selected salvage chemotherapy:

Prior therapy and response:

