13.8. Safety Analysis

The safety analysis set (SAF) includes all subjects receiving at least 1 dose of study treatment (quizartinib or salvage chemotherapy).

Safety evaluation will be based mainly on AEs, clinical laboratory test results, physical examination results, vital signs, ECG results and ECOG performance scores. Descriptive statistics will be used to summarize safety data. All safety data will be summarized by treatment.

All summaries of AEs will include only treatment-emergent events unless otherwise stated. Adverse events will be categorized by system organ class and preferred term using the most current MedDRA dictionary, and will be graded according to NCI CTCAE v4.03.

Additional safety analysis for subjects in post-HSCT quizartinib arm may be performed.

The safety data will also be summarized for each sub-group defined according to the following:

- Age (< 60 and ≥60 years)
- Age (<65, ≥65 to <75, and ≥75 years)
- Sex at birth (male and female)
- Race (Caucasian, Black or African American, Asian, and Other)
- Ethnicity (Hispanic or Latino, Non-Hispanic or Latino)

- Concomitant use of strong CYP3A4 inhibitor (yes and no)
- Baseline ECOG performance score (0, 1, ≥ 2)
- Baseline body mass index (<18.5, 18.5 to <25, 25 to <30, ≥ 30 kg/m²)
- Prior allogeneic HSCT (yes and no)

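### Section 13.8 plans descriptive adverse-event summaries by arm with no exposure-adjusted or common-window analysis, although AE observation time follows treatment length and differs by design

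*Combined protocol and SAP*

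**What the plan says.** Section 13.8 plans descriptive statistics for safety and states "All safety data will be summarized by treatment". Treatment-emergent AEs are classified by system organ class and preferred term and graded by CTCAE. The safety subgroups are age, sex, race, ethnicity, strong CYP3A4 inhibitor use, ECOG score, body mass index and prior allogeneic HSCT. Control regimen and chemotherapy intensity are not among them. An additional safety analysis of post-HSCT quizartinib is optional. Section 13.2 tabulates drug administration but does not use it as a denominator for AEs.

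The rules that set how long AEs are observed are elsewhere:

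- Section 8 evaluates AEs "until 30 days after the last dose of study treatment".
- Section 5.8, Table 5, footnote i: "MEC and FLAG-IDA are administered for up to 2 cycles, depending on response and safety assessments".
- Section 5.1.2, for subjects on quizartinib or LoDAC: "treatment should continue until there is no longer clinical benefit from therapy, or until unacceptable toxicity occurs".
- Section 5.6.4.5 allows quizartinib to resume 30 to 100 days after transplant, in that arm only. Section 8.8 requires AEs to be recorded again once it restarts.

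**The concern.** Because collection stops 30 days after the last dose, observation time follows treatment time. Part of the control arm has a short, fixed course; the quizartinib arm does not. The percentage of subjects with at least one event rises with time observed even when the underlying rate is identical, so a by-arm percentage mixes toxicity with observation time.

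Post-HSCT resumption can widen the difference. Section 5.2.5 expects about 35% of subjects to be bridged to HSCT. It also cites a post-HSCT maintenance study in which 10 of 13 subjects took quizartinib for more than a year.

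What is at stake is the safety half of the benefit-risk comparison. If percentages are the only display, a reader cannot tell longer exposure from higher risk, and a truly lower rate on quizartinib may not show.

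**Working it through.** **The plan's own figures.** The safety sections state no number to reproduce. The checkable design figure is 280 deaths for 90% power (Section 13.3). A fixed design at HR 0.65, 2:1 allocation and two-sided 0.05 needs (1.960 + 1.282)² / [(2/9)(ln 0.65)²] = 255 deaths. Adding the Lan-DeMets O'Brien-Fleming interim at 140 deaths (z = 2.963, then 1.969) and the 10% conditional-power bound under the current trend (z = 0.751, treated as binding) gives 90.0% power at 280. The figure stands, and this point does not touch it.

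**Observation windows for one cycle of MEC or FLAG-IDA.** Two readings are possible.

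- From the last dose, as Section 8 says: MEC dosing ends on Day 5 and FLAG-IDA on Day 6 (Section 5.6.4.2), so the window closes at 5 + 30 = Day 35 or 6 + 30 = Day 36.
- From the end of the cycle, roughly the Day 29 end-of-treatment visit (Section 6.2.5.1): 28 + 30 = 58 days. Two cycles give 56 + 30 = 86 days.

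**Assumptions.** The documents give no AE rates, treatment durations or LoDAC share. I assume a constant rate λ of first events per 28 days, equal in both arms unless stated. Total quizartinib windows, including the 30-day tail, are taken as 56 to 168 days.

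**Formula.** Crude incidence = 1 − exp(−λ × days/28).

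**Equal rates, λ = 0.10.** The 112-day value is 1 − exp(−0.40) = 33.0%. The chemotherapy values are 1 − exp(−0.10 × 35/28) = 11.8%, 1 − exp(−0.10 × 58/28) = 18.7% and 1 − exp(−0.10 × 86/28) = 26.4%.

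| Quizartinib window | Crude % | Ratio to 35 days (11.8%) | Ratio to 58 days (18.7%) | Ratio to 86 days (26.4%) |
|---|---|---|---|---|
| 84 days | 25.9 | 2.21 | 1.39 | 0.98 |
| 112 days | 33.0 | 2.81 | 1.76 | 1.25 |
| 168 days | 45.1 | 3.84 | 2.41 | 1.71 |

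The true rate ratio is 1.00 in every cell. For 112 against 58 days, the ratio runs from 1.84 at λ = 0.05 to 1.42 at λ = 0.40.

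**LoDAC dilution.** Suppose a share of controls receives LoDAC with the same 112-day window. At 25%, control incidence is 0.75 × 18.7 + 0.25 × 33.0 = 22.3% (ratio 1.48). At 50% it is 25.8% (ratio 1.28).

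**Short quizartinib exposure.** A 56-day window gives 1 − exp(−0.20) = 18.1%. Against 18.7% at 58 days there is no excess. Against 11.8% at 35 days a gap remains.

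**Masking.** Let the chemotherapy rate be twice that of quizartinib (0.20 against 0.10). With 58 against 112 days, crude incidence is 33.9% on chemotherapy and 33.0% on quizartinib, so a twofold difference disappears. With 35 against 112 days it is 22.1% against 33.0%, so the direction reverses.

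**With the fix.** Under these assumptions a person-time rate recovers λ in each arm whatever the window, and a shared window gives equal percentages when rates are equal.

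**The case against.** Several stronger readings are tempting, and the documents do not support them.

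- **That the plan confines itself to crude incidence.** Section 13.8 names no metric and rules none out. Section 13.4 sends OS sensitivity detail to a statistical analysis plan, and Section 5.1 refers to a DMC charter and an Interim Analysis Plan; none of these is in the supplied text. What can be said is that no exposure-adjusted or common-window analysis is specified.
- **That quizartinib will look more toxic.** This depends on realised exposure. Early stopping on quizartinib, or a second chemotherapy cycle, can remove the effect. Long windows are also limited by survival: the planned quizartinib median is 6 months, and Section 5.6.5 expects about 80% of deaths in long-term follow-up, after AE collection has closed.
- **That the contrast applies to the whole control arm.** LoDAC is open-ended like quizartinib, so the pooled arm is less unequal than MEC or FLAG-IDA alone.
- **That the interim decision would be distorted.** In Section 13.10, safety and benefit-risk enter the DMC's decision on stopping once conditional power crosses the 10% futility boundary. That is narrower than the interim as a whole.

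Two technical objections also stand. A person-time rate assumes a roughly constant hazard; if chemotherapy toxicity clusters soon after dosing, dividing by a short time at risk inflates the chemotherapy rate. Death is a competing event that the illustration ignores, and it matters at planned medians of 3.9 and 6 months.

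The plan already covers part of the ground: drug administration is tabulated, and a post-HSCT safety analysis is permitted. But the tabulation is not linked to AEs, and the post-HSCT analysis is optional.

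**Conclusion.** The point holds as a gap in specification. AE observation time differs by design between quizartinib and MEC/FLAG-IDA, and Section 13.8 commits to nothing that separates exposure from risk. By-arm percentages can mislead in either direction.

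With an assumed equal rate of 0.10 per 28 days and a 112-day quizartinib window, the spurious gap is 33.0 − 18.7 = 14.3 percentage points against a 58-day window and about 21 points against 35 days. It is smaller with more LoDAC and absent when the windows match. The sizes rest on assumed rates, exposures and LoDAC shares; the direction in the actual trial cannot be known from the documents. Since realised exposure is unknown in advance, prespecifying the analyses is the sensible course. This is an inexpensive improvement to the safety reporting. It is not a flaw in the primary analysis.

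**What to change.** In Section 13.8, for TEAEs, Grade 3 or higher TEAEs, SAEs and AEs of interest, add:

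1. Exposure-adjusted incidence by arm: subjects with a first event per subject-month at risk. Count only time during which AEs are collected, so that the transplant gap off quizartinib is not counted as time at risk.
2. A crude comparison in a window that both arms are observed through under the Section 8 rule, such as Cycle 1 (first 28 days). Even a subject given a single dose on Day 1 is followed to 1 + 30 = Day 31, apart from death, withdrawal or an early move to other AML therapy. A 58-day window would not do: counted from the last dose, a one-cycle MEC or FLAG-IDA subject is observed only to Day 35 or 36.
3. A split by pre-selected chemotherapy intensity. It is already a stratification factor recorded for both arms, so like can be compared with like.
4. Post-HSCT quizartinib exposure and its AEs shown separately, as a planned table and not an optional one.

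Also state whether the 30 days run from the last dose or from the end-of-treatment visit.

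The cost is a few extra tables from data already collected, with no change to conduct, sample size or alpha. The drawback is the constant-hazard assumption in item 1, so it should always be read together with item 2.

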13.9. Additional Analyses

Pharmacogenomic analyses are described in Section 10, and pharmacoeconomic analyses in Section 11.

13.10. Interim Analysis

The study design provides for one formal interim analysis when 50% (140) of the final number of events have been observed. At the discretion of the DMC, one of the following recommendations will be made at this interim analysis:

- Termination of the study for futility.
- Termination of the study for efficacy.
- Continuing the study as planned.

The DMC may only recommend that the Sponsor discontinue the study early only for either efficacy or futility.

The efficacy boundary will be based on the O'Brien-Fleming efficacy boundary derived from the Lan and DeMets error spending function, and the appropriate amount of α will be spent to ensure that the overall 1-sided type I error remains at 0.025. The futility boundary will be based on CP. At the time of the interim analysis, should the CP cross the futility boundary of 10%, the DMC will decide whether to recommend stopping the study. This decision will be based on the totality of information available at the interim analysis, including results of sensitivity analyses, secondary efficacy endpoint analyses, safety analyses, and benefit-risk analyses.

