The study will utilize a group sequential design with 1 interim analysis at 0.5 information fraction (ie, approximately 50% of planned number of events). The target sample size will be approximately 363 subjects, randomized in a 2:1 ratio to receive quizartinib monotherapy (242 subjects) or salvage chemotherapy (121 subjects). One formal interim analysis will be performed by an independent statistical analysis center (SAC) and evaluated by an independent data monitoring committee (DMC), according to statistical procedures defined a priori. Based on the results of the interim analysis, the DMC may recommend that the study be terminated early for futility or for efficacy, or continue as planned. The tasks performed by the SAC and DMC are described in the DMC charter and Interim Analysis Plan.

Prior to randomization, the Investigator will pre-select a salvage chemotherapy regimen for each subject; options include low dose cytarabine (LoDAC); mitoxantrone, etoposide, and intermediate-dose cytarabine (MEC); or fludarabine, cytarabine, and granulocyte colony stimulating factor (G-CSF) with idarubicin (FLAG-IDA).

Screening

During the 14 day screening period, subjects will undergo medical history evaluation, physical examination, vital sign determination, Eastern Cooperative Oncology Group (ECOG) performance status assessment, chest X-ray, concomitant medication assessment, blood and urine sampling for laboratory tests, ECG monitoring, and bone marrow aspiration/biopsy to confirm FLT3-ITD status and confirm diagnosis. Subjects will undergo multiple gated acquisition (MUGA) scans or echocardiography (ECHO).

STUDY POPULATION

Inclusion Criteria

To be able to participate in this study, candidates must meet the following criteria at screening or other specified time point:

1. Provision of written informed consent approved by the Institutional Review Board (IRB) or Independent Ethics Committee (IEC) with privacy language in accordance with national regulations [eg, Health Insurance Portability and Accountability Act (HIPAA) authorization for US sites] prior to any study-related procedures, including withdrawal of prohibited medications if applicable.
2. Age ≥ 18 years or the minimum legal adult age (whichever is greater) at the time of informed consent.

3. Morphologically documented primary AML or AML secondary to myelodysplastic syndrome (MDS), as defined by World Health Organization criteria, as determined by pathology review at the study site.

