Safety evaluation will be based mainly on AEs, clinical laboratory test results, physical examination results, vital signs, ECG results and ECOG performance scores. Descriptive statistics will be used to summarize safety data. All safety data will be summarized by treatment (quizartinib or salvage chemotherapy). The safety data will also be summarized for pre-defined sub-groups.

All summaries of AEs will include only treatment-emergent events unless otherwise stated. Adverse events will be categorized by system organ class and preferred term using the MedDRA dictionary (version 14.1), and will be graded according to NCI CTCAE v4.03.

Additional safety analysis for subjects in post-HSCT quizartinib arm may be performed.

Additional Analyses

AML mutations, pharmacogenomic, pharmacoproteomic, and pharmaco-economic analyses will be performed.

Interim Analysis

The study design provides for one formal interim analysis when 50% (140) of the final number of events have been observed. At the discretion of the DMC, one of the following actions will occur at this interim analysis:

- Termination of the study for futility
- Termination of the study for efficacy
- Continuing the study as planned

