5. STUDY DESIGN

5.1. Overall Study Design and Plan

This is a Phase 3, randomized, open-label, 2-arm study to compare the effect of quizartinib monotherapy and salvage chemotherapy on OS in subjects with FLT3-ITD(+) AML that is refractory or relapsed within 6 months, after first-line therapy with or without consolidating HSCT. The control treatment is a limited choice of one of three standard chemotherapy regimens (low dose cytarabine [LoDAC]; mitoxantrone, etoposide, and intermediate-dose cytarabine [MEC]; or fludarabine, cytarabine, and granulocyte-colony stimulating factor (G-CSF) with idarubicin [FLAG-IDA]) which are widely used to treat patients with AML. Prior to randomization, the Investigator will pre-select one of the three salvage chemotherapy regimens for each subject; doses and the duration of study treatments are outlined in Section 5.6.4.2.

The study will utilize a group sequential design with 1 interim look at 0.5 information fraction (ie, 50% of planned number of events [deaths]). The target sample size will be approximately 363 subjects, randomized in a 2:1 ratio to receive quizartinib monotherapy (242 subjects) or salvage chemotherapy (121 subjects). One formal interim analysis will be performed by an independent statistical analysis center (SAC) and evaluated by an independent data monitoring committee (DMC), according to statistical procedures defined a priori. Based on the results of the interim analysis, the DMC may recommend that the study be terminated early for futility or for efficacy, or continue as planned. The tasks performed by the SAC and DMC are described in the DMC charter and Interim Analysis Plan.

If the study is positive at the pre-specified interim or final analysis, the sponsor may allow subjects who did not receive quizartinib to cross-over to the quizartinib monotherapy arm after database lock if the safety parameters in the eligibility criteria are met (see Section 5.4). The study will be unblinded after database lock.

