5.5. Study or Site Termination

If the Sponsor, the Investigator, the clinical monitor, United States (US) Food and Drug Administration (FDA) or other Competent Authority officials discover conditions during the study indicating that the site's participation should be terminated, this action may be taken after appropriate consultation between the Sponsor and the Investigator. Conditions that may warrant termination of the study include, but are not limited to:

- Discovery of an unexpected, serious, or unacceptable risk to subjects enrolled in the study
- Sponsor's decision to suspend or discontinue testing, evaluation, or development of the study drug
- Investigator's failure to comply with pertinent US FDA or regional Health Authority regulations and ICH (International Conference on Harmonisation of Technical Requirements for Registration of Pharmaceuticals for Human Use) guidelines
- Insufficient compliance with protocol requirements

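### Section 13.10 gives the DMC no stated ground to recommend stopping for harm while conditional power is above 10% and, read literally, none at any time

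*Combined protocol and SAP*

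**What the plan says.** Section 13.10 lists three possible recommendations at the single formal interim analysis: stop for futility, stop for efficacy, or continue. It then adds: "The DMC may only recommend that the Sponsor discontinue the study early only for either efficacy or futility". The list is tied to the interim analysis; the added sentence is not.

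The same three options appear elsewhere:

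- Synopsis, Study Design, repeated in Section 5.1: "the DMC may recommend that the study be terminated early for futility or for efficacy, or continue as planned".
- Synopsis, Interim Analysis: "At the discretion of the DMC, one of the following actions will occur at this interim analysis", followed by the three options.
- Section 13.3: "the DMC may recommend 3 potential study options", again the same three.

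Safety appears in the DMC's decision at one point. Section 13.10 says that "should the CP cross the futility boundary of 10%, the DMC will decide whether to recommend stopping the study", and that this decision weighs all the information available, including safety and benefit-risk analyses.

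Two other places bear on the point. Section 5.5 gives, among conditions that may warrant terminating the study, "Discovery of an unexpected, serious, or unacceptable risk to subjects enrolled in the study". It names the sponsor, investigator, clinical monitor and authorities, but not the DMC. Section 5.1 refers the DMC's duties elsewhere: "The tasks performed by the SAC and DMC are described in the DMC charter and Interim Analysis Plan". Neither of those two documents is part of the material reviewed.

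**The concern.** The DMC is the body that evaluates survival by arm. Under Section 5.6.5 the sponsor sees aggregate efficacy data only with the arms combined. It has no individual long-term follow-up, which begins 30 days after study treatment ends and in which about 80% of the planned deaths are expected. AE evaluation also ends 30 days after the last dose (Section 8), and Section 8.10.1 keeps deaths from disease progression out of AE and SAE recording.

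A comparative harm could therefore be visible to the DMC and not to the sponsor, while the sentence in Section 13.10 limits the DMC's stopping grounds to efficacy and futility. QT prolongation is a recognised risk of the drug (Section 8.5), so the DMC's safety remit matters in practice.

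**Working it through.** **1. The texts side by side.** No list gives the DMC a safety option. On the narrow reading, the sentence governs only the 140-death look; safety then counts only after CP reaches 10%, so above 10% there is no stated harm ground. On the literal reading, the same holds before that look and during the 140 deaths after it.

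**2. Reproducing the plan's own figure.** Section 13.3 states: "A total of 280 events (deaths) are necessary to meet a power requirement of 90" per cent. Inputs from Sections 13.3 and 13.10: HR 3.9/6 = 0.65, allocation 2:1, 140 of 280 deaths, one-sided alpha 0.025, Lan-DeMets O'Brien-Fleming spending, CP 10% for futility.

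- Efficacy bounds: z = 2.963 at 140 deaths and z = 1.969 at 280.
- Drift at 280 deaths: sqrt(280 × 2/9) × −ln 0.65 = 3.398.
- CP at interim value z = 1 − Φ[(1.969 − z√0.5 − 0.5θ)/√0.5], where θ is the drift assumed for the rest of the trial.
- Current-trend form (θ = z/√0.5), stopping whenever CP is below 10%: power at 280 deaths is 90.0%, and 90% power needs 280.0 deaths. This matches the plan.
- Design-effect form (θ = 3.398): power at 280 is 92.4%, and 90% power needs only 256 deaths. This does not match.

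The protocol does not name the CP form; the current-trend form is inferred from this match.

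**3. Where CP equals 10%.** SE of log HR at 140 deaths = 1/sqrt(140 × 2/9) = 0.179; its reciprocal is 5.578.

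- Current trend: (1.969 − 1.414z)/0.707 = 1.282, so z = 0.751 and the observed HR is exp(−0.751/5.578) = 0.874.
- Design effect: (1.969 − 0.707z − 1.699)/0.707 = 1.282, so z = −0.900 and the observed HR is exp(0.900/5.578) = 1.175.

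**4. Chance that a survival detriment opens a futility decision at the look.** P = Φ(z boundary + 5.578 × ln HR).

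| True HR | Current trend | Design effect |
|---|---|---|
| 1.0 | 77% | 18% |
| 1.1 | 90% | 36% |
| 1.2 | 96% | 55% |
| 1.5 | 99.9% | 91% |

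For example, at HR 1.1 under current trend: Φ(0.751 + 0.532) = Φ(1.283) = 0.90.

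**5. Chance of landing where only continuation is listed.** The efficacy bound corresponds to an observed HR of exp(−2.963/5.578) = 0.588. Between 0.588 and 0.874 (current trend) neither boundary is crossed, and the only option the lists support is to continue. At the design HR of 0.65 the mean interim z is 5.578 × 0.431 = 2.403, so the chance of falling in that zone is Φ(2.963 − 2.403) − Φ(0.751 − 2.403) = 0.712 − 0.049 = 0.66. This measures how often a non-survival safety problem at the look would lack a listed ground, not how likely such a problem is.

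**6. What the sponsor cannot see.** 0.80 × 280 = 224 deaths are expected in the follow-up withheld from it, leaving 56 before that point.

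**The case against.** The strongest reply is context. The sentence sits under the heading Interim Analysis, between a list for that look and the boundaries for that look. It may simply describe the outcomes of one formal efficacy analysis. The DMC's duties are assigned to a charter and an Interim Analysis Plan that could give a full safety remit. The trial can also be stopped for harm without the DMC, through Section 5.5. Section 8.10.4 requires all SAEs and deaths to be reported whatever their cause, and QTcF prolongation of Grade 3 or higher within 24 hours, so the sponsor learns of fatal and non-fatal events up to 30 days after treatment. A survival detriment at the look is largely caught by the futility rule, with safety and benefit-risk considered.

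Most of this stands, and it limits the point. Three stronger inferences are therefore not supported:

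- A reader might infer that the trial cannot be stopped for harm. Section 5.5 provides a route.
- A reader might infer that the DMC has no safety remit. That cannot be judged without the charter, and silence in the protocol does not establish it.
- A reader might take the 224 of 280 deaths as the size of the defect. That figure describes what the sponsor cannot see; it does not say how often the DMC would be prevented from acting.

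The reply does not remove the point. The narrow reading still leaves no listed harm ground at the look while CP is above 10%. The sponsor's route does not give it a comparison of survival by arm. If the charter does allow a safety stop, the protocol sentence as worded conflicts with it.

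**Conclusion.** The point holds in a limited form and should be fixed. Section 13.10 states a rule that leaves the DMC no stated ground to recommend stopping for harm while CP is above 10%; taken literally, it leaves none at any time. An interim-only meaning is plausible, but the sentence does not say so.

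The residual gap is comparative harm that the sponsor cannot see by arm, and non-survival harm while CP is above 10%. Survival harm at the look is mostly covered if CP follows the current trend (about 90% at a true HR of 1.1). It is covered much less well under the design-effect form (about 36%), although that form does not reproduce the plan's power. If the design HR of 0.65 is true, there is about a 66% chance that the look falls between the two boundaries under current trend, where the lists offer only continuation.

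These figures assume proportional hazards, the usual normal approximation with 2:1 allocation, and a look at exactly 140 deaths. Confidence is medium, because the charter and Interim Analysis Plan have not been seen. Type I error and power are not affected.

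**What to change.** Replace the sentence in Section 13.10 with: *At the formal interim analysis, the DMC may recommend stopping for efficacy or futility; this does not limit the DMC's ability to recommend stopping or modifying the study for safety at this or any other review it holds.*

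Align the option lists in the synopsis (Study Design and Interim Analysis), Section 5.1 and Section 13.3. Reconcile the result with Section 5.5, the DMC charter and the Interim Analysis Plan.

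The cost is one sentence, four matching edits and a check against two existing documents. The wording does not presuppose extra reviews, and no further unblinded survival looks are proposed. A stop for harm spends no alpha: the one-sided 0.025, the 280 deaths and the look at 140 deaths stay as they are.
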